6/14/2021

Pleural Manometry for the Characterization of
Spontaneous and Tension Pneumothorax

NCT04630301

Date: 06/14/2021

Principal Investigator: [name]

Application Number: IRB00256185

JHM IRB - eForm A – Protocol

- **Use the section headings to write the JHM IRB eForm A, inserting the appropriate material in each. If a section is not applicable, leave heading in and insert N/A.**
- **When submitting JHM IRB eForm A (new or revised), enter the date submitted to the field at the top of JHM IRB eForm A.**

1. Abstract

A pneumothorax is defined as the presence of air within the pleural space. Patients can be asymptomatic, have mild dyspnea, or significant chest pain and dyspnea, and even hemodynamic instability in the case of a tension pneumothorax (TP).¹ The historical teaching for the cause of hemodynamic instability has been increased pressures within the pleural space causing a shift of the mediastinum, “kinking” of the inferior vena cava and a reduction in cardiac output. Expert guidelines define TP as when the intrapleural pressure (Ppl) is greater than atmospheric pressure for much of the respiratory cycle.² Therefore, it follows that Ppl in patients without tension remains below atmospheric pressure for much of the respiratory cycle. However, these manometric definitions remain controversial as Ppl in TP has never been measured and data on Ppl on hemodynamically stable patients is limited. There remains a gap in our current understanding of the pathophysiology of these disease processes. Exploring this unknown can be of clinical significance as pleural manometry is being employed in patients with pleural effusions to guide management. By using recently demonstrated pleural manometric techniques, this study aims to characterize the intrapleural pressures in patients with pneumothorax.

2. Objectives

Primary objectives:

1. Describe the intrapleural pressure throughout the respiratory cycle in patients with pneumothorax.

Secondary objectives:

1. Demonstrate a relationship between initial intrapleural pressure and presence of persistent air leaks, need for prolonged chest tube drainages, pleurodesis, intrabronchial valve (IBV) placement, and/or video-assisted thorascopic surgery (VATS).

3. Background

The rate of hospitalization for spontaneous pneumothorax among people age 14 or older is approximately 227 per million.³ Spontaneous pneumothorax in the absence of trauma can be further classified as primary spontaneous pneumothorax (PSP) or secondary spontaneous pneumothorax (SSP) based on the absence or presence of underlying structural lung disease, respectively. Though recent studies suggest that in some cases conservative management with close observation is an acceptable treatment, definitive evacuation remains a cornerstone of management for patients who are symptomatic or who have a large pneumothorax.⁴ Intrapleural

Date: 06/14/2021

Principal Investigator: [name]

Application Number: IRB00256185

air can be removed by either needle aspiration or introduction of a watersealed catheter into the pleural space. In the event of TP, emergent chest thoracostomy is preferred. In all cases, the goal of treatment remains to re-expand the affected lung, after which the catheter may be removed. If the visceral pleural defect is not healed after 5 days, it is deemed a persistent air leak. In these cases, the chest tube is maintained and more aggressive measures such as pleurodesis, placement of an IBV, or VATS are performed. Unfortunately, there is currently no method to predict which patients will require these more invasive procedures.

The lack of prognostic indicators is not the case in pleural effusions, however. Pleural manometry has been shown to be a useful tool in the management of patients with effusions. Doelken et al. described using an overdamped water manometer or an electronic transducer connected to a thoracentesis catheter for the direct measurement of Ppl with similar accuracy.⁵ Traditionally, thoracenteses are aborted after onset of dyspnea or cough, all fluid is drained, or 1L of fluid has been removed. This 1L limit exists to avoid the feared complication of reexpansion pulmonary edema. However, monitoring of Ppl during drainage and aborting the procedure once Ppl drops below -20 cmH₂O allows for safe drainage of often larger volumes.⁶⁻⁷ Furthermore, Lan et al. demonstrated that Ppl could diagnose non-expandable lung and predict pleurodesis failure in patients with malignant effusion.⁸ Lee et al, recently reported the use of a simple, in-line, digital manometer to measure Ppl in patients with pleural effusion.⁹

Routine use of pleural manometry in the evaluation and management of pneumothorax has not yet been adopted, likely due to the historical difficulty in obtaining measurements and the uncertain clinical benefit they provided. Harrejón et al. found that Ppl in spontaneous pneumothorax was greater in patients that required prolonged drainage.¹⁰ These results were later supported by Kaneda et al who also demonstrated the practicality of measuring Ppl in pneumothorax. Their measurements required only up to 30 seconds by using an electronic manometer connected to an intrapleural catheter.¹¹ Still to date, Ppl in TP have yet to be reported.

4. Study Procedures

- a. Patients admitted with spontaneous, iatrogenic, or tension pneumothorax referred to the section of Interventional Pulmonology will be recruited. Using standard sterile technique, a 14fr catheter will be inserted into the pleural space. An electronic manometer (Compass, Medline Industries, Inc.) will be connected in-line to the introducer needle and Ppl will be recorded for 3-5 respiratory cycles. The catheter will then remain in place per routine standards of practice. Outcome data of patients will be collected including indication for chest tube placement, duration of chest tube placement, need for pleurodesis, IBV, and referral for VATS. Patient data will be de-identified and stored on the SAFE (or equivalently password-protected/secure) desktop at each local institution
- b. Johns Hopkins' Interventional Pulmonology (IP) research team will act as the lead coordinating site and [name] will act as the overall study Principal Investigator. This group already has the contact information for planned non-JHU sites (names & emails/phone numbers for PI & study coordinators at each site). The IP research team will be responsible for ensuring each participating institution has IRB approval and up-to-date human subjects' compliance training.. The JHU IP research team will track IRB approval dates and store copies of each non-Hopkins affiliated site's documents (e.g. IRB approval letters, protocols, consent form templates) on a JHU-password-protected shared drive. Dates and protocol versions of materials sent to each site will also be recorded on a spreadsheet to ensure all sites are using the most current materials. If any local IRB requested edits (besides changing PI & institution

Date: 06/14/2021

Principal Investigator: [name]

Application Number: IRB00256185

names/contact) are needed, those will be reviewed & approved by JHU's IP research team prior to submission.

- c. De-identified data from all sites will be recorded into a JHU-hosted REDCap database. This database includes logging and data lock features to ensure accuracy and compliance. In addition, we will setup “data access groups” which will not only restrict sites to seeing only their own data, but also ensure data is organized sufficiently by site. Any relevant paper source documents will be kept in a locked cabinet at each institution’s site. Scanned or electronic copies of source documents will be kept on a secured, password-protected institution-hosted drive (e.g. SAFE desktop for JHU).
- d. Adverse Event and Protocol Deviation form will be included in the REDCap data entry forms for this study so that sites can easily report an events/ deviations (these forms can be setup with email alerts to the JHU PI & research team for immediate notification). JHU’s IP research team will determine if immediate local IRB notification is required or if events/ deviations can be sent with annual progress reports.
- e. No biospecimens will be collected.
- f. Patients will be enrolled over the course of 1 year. The study will not impact length of hospitalization.
- g. This is a nonblinded study.
- h. Patients will continue to receive standard of care treatments. This study may delay catheter placement by mere seconds to accommodate for Ppl measurements, this delay is negligible and will not impact clinical outcomes as even in the case of tension the pleural air will be evacuated via the introducer needle.
- i. This study does not include a placebo group.
- j. Participant removal criteria include pneumothorax in which Ppl cannot be reliably measured within 30 seconds.
- k. Participants removed from the study will continue to receive standard-of-care treatment.
- l. JHU will conduct periodic monitoring of study data (e.g. comparing paper documents to REDCap entries and ensuring source documents like EPR reflect the same information recorded). If necessary, due to continued covid-19 restrictions, these monitoring visits may be performed via Zoom or MS Teams provided sites are able to share EPR screens and scanned paper documents for comparison.

5. Inclusion/Exclusion Criteria

Criteria for recruitment into this study include patients aged 18 or older admitted with clinical or radiographic evidence of new pneumothorax who are referred to Interventional Pulmonology for needle aspiration or tube thoracostomy. TP will be defined as a pneumothorax that results in mean arterial pressure <65 or systolic BP < 90.

Exclusion criteria include bilateral pneumothorax and pregnancy.

6. Drugs/ Substances/ Devices

No medical drugs, substances, or devices are being studied.

7. Study Statistics

- a. Primary outcome variables: Inspiratory Ppl, Expiratory Ppl, and Mean Ppl.
- b. Secondary outcome variables: Duration of chest tube placement, referral for pleurodesis, IBV placement, and/or referral for VATS.

Date: 06/14/2021

Principal Investigator: [name]

Application Number: IRB00256185

- c. Statistical plan: A student's t-test will be used to determine statistical significance in differences of Ppl between SP and TP. A student's t-test will be used to determine statistical significance in differences of Ppl in the secondary outcomes listed above. A sample size of 100 SP and 25 TP will be used based on expected incidence of disease in recruitment period. Enrollment will be competitive across all sites and the Coordinating Center (JHU's IP research team) will immediately alert PIs and Study Coordinators at the other sites if enrollment is paused or completed.
- d. Early stopping rules: Consistent inability to measure Ppl in TP. If study is stopped early, all sites will immediately be notified by JHU's IP research team to terminate enrollment.

8. Risks

- a. Enrolled patients will be only those already planned to receive chest tubes or needle aspiration; therefore, this study poses the same risks as these standard procedures. These risks include bleeding, infection, and local tissue damage. The study may delay evacuation of pneumothorax up to 30 seconds while Ppl are being recorded. These risks are independent of participation or non-participation in our study. No provisions are made for a research study-specific injury to the subject.
- b. Risks will be mitigated by using the same standard of care for chest tube or needle aspiration. Overall, the delay in chest tube placements will be minimized and negligible by limiting measurement time to 30 seconds.
- c. Any unanticipated problems will be reported to the local principal investigator and relayed to their local IRB. In addition, any adverse events or protocol deviations will be relayed to the study Principal Investigator and JHU research team (as lead coordinating site). The Principal Investigator, Co-Investigators, and Study Coordinators will meet as needed to review adverse effects and share information with all sites for reporting (if required by their local IRBs).
- d. As participant health data will be collected, there is a risk to confidentiality breach. However, this is mitigated by de-identifying patient data and storing information on SAFE desktops and a JHU-hosted REDCap database.
- e. The study does not pose financial risks to participants.

9. Benefits

There are no additional benefits to study participants, as those who do not wish to be involved in the study will still undergo standard of care pneumothorax evacuation. However, society will benefit from the increased pathophysiologic understanding of pneumothorax as results may guide future management.

10. Payment and Remuneration

This study offers no payment or renumeration to participants.

11. Costs

This study incurs no increased costs to the participants.

¹ Sahn SA, Heffner JE. Spontaneous pneumothorax. *N Engl J Med*. 2000;342(12):868-874.

Date: 06/14/2021

Principal Investigator: [name]

Application Number: IRB00256185

² MacDuff A, Arnold A, Harvey J. Management of spontaneous pneumothorax: British Thoracic Society pleural disease guideline 2010. *Thorax* 2010;65:ii18-ii31.

³ Bobbio A, Dechartres A, Bouam S, et al. Epidemiology of spontaneous pneumothorax: Gender-related differences. *Thorax*. 2015;70(7):653.

⁴ Brown SGA, Ball EL, Perrin K, et al. Conservative versus interventional treatment for spontaneous pneumothorax. *N Engl J Med*. 2020;382(5):405-415.

⁵ Doelken P, Huggins JT, Pastis NJ, Sahn SA. Pleural manometry: technique and clinical implications. *Chest*. 2004;126(6):1764-1769.

⁶ Feller-Kopman D, Berkowitz D, Boiselle P, Ernst A. Large-volume thoracentesis and the risk of reexpansion pulmonary edema. *Ann Thorac Surg*. 2007;84(5):1656-1661.

⁷ Light RW, Jenkinson SG, Minh VD, George RB. Observations on pleural fluid pressures as fluid is withdrawn during thoracentesis. *Am Rev Respir Dis*. 1980;121(5):799-804.

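### Do sections 4h and 8a contradict each other on whether air is evacuated while pleural pressure is being recorded?

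*Combined protocol and SAP*

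**What the plan says.** Section 4a has a catheter inserted, a manometer connected to the introducer needle, and pressure (Ppl) recorded over 3 to 5 respiratory cycles, after which the catheter stays in.

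Section 4h describes the effect of this on care: "This study may delay catheter placement by mere seconds to accommodate for Ppl measurements". It calls the delay negligible because "even in the case of tension the pleural air will be evacuated via the introducer needle".

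The risk section describes the delay twice. Section 8a: "The study may delay evacuation of pneumothorax up to 30 seconds while Ppl are being recorded". Section 8b: "Overall, the delay in chest tube placements will be minimized and negligible by limiting measurement time to 30 seconds".

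Section 8a first lists the ordinary procedural hazards ("These risks include bleeding, infection, and local tissue damage"), then mentions the measurement delay, then adds "These risks are independent of participation or non-participation in our study".

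Two safeguards apply. Section 4j: "Participant removal criteria include pneumothorax in which Ppl cannot be reliably measured within 30 seconds". Section 4k: "Participants removed from the study will continue to receive standard-of-care treatment".

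The primary outcomes in section 7a are inspiratory, expiratory and mean Ppl. The secondary objective in section 2 relates the initial pressure to later course. Section 7c compares Ppl between 100 spontaneous and 25 tension cases by t-test.

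**The concern.** In 4h the thing delayed is the catheter, and the reassurance is that air escapes by the needle. In 8a the thing delayed is evacuation. If air does not leave during the recording, the reason given in 4h does not cover the seconds that the study adds. That matters most in tension, which section 5 defines by low blood pressure and for which section 3 describes emergent treatment. If air does leave during the recording, 8a is wrong as written, and the later cycles may no longer show the initial pressure.

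The second possibility is the statistical one. Ppl is the primary outcome and the predictor in the secondary objective. If sites handled the needle differently, or handled tension cases differently from the rest, the t-test could be comparing readings taken under different conditions.

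Two further wordings add to the impression of disorder. Section 4a names catheter insertion before the needle reading, although 4h and 8b have the reading holding up the catheter or tube. And the sentence in 8a about risks not depending on participation comes straight after a delay that exists only because of the study.

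**Working it through.** The plan states no figure that needs reproducing. The main check is to set the passages side by side.

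**What is delayed**

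| Section | What waits | How long | When air leaves |
|---|---|---|---|
| 4h | catheter placement | seconds | by the needle; timing not stated |
| 8a | evacuation | up to 30 s | not while the delay lasts |
| 8b | chest tube placement | measurement limited to 30 s | not stated |

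**Can all three be true together?** Take the sequence: needle in, reading, evacuation by the needle, catheter. Evacuation waits for the reading, as in 8a. The catheter waits as well, as in 4h and 8b. Air leaves by the needle before the catheter is in, as in 4h. No sentence in the three sections is false under this sequence. It is used here only to test compatibility, not recommended as a clinical order.

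**What is left over?** Under that sequence the needle argument in 4h covers the time after the reading, not the reading itself. For the reading, the protocol relies on the time cap in 8b, with removal (4j) and standard care afterwards (4k).

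**Section 4a.** An introducer needle serves to introduce the catheter. The first sentence on insertion therefore reads naturally as naming the procedure, and the next as describing a step within it.

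**Initial pressure.** Section 4a describes one recording per patient, and no later reading is planned that could be confused with it. The only passage linking recording to evacuation in time is 8a, and it puts recording first. The contrary reading needs the words *during recording* to be added to 4h.

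**Duration.** Recording time in seconds = cycles × 60 / breaths per minute. The cycles (3 to 5) come from 4a and the 30-second limit from 4j, 8a and 8b. The documents give no breathing rate, so the rates below are assumptions.

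- 20 to 30 per minute: shortest 3 × 60/30 = 6 s; longest 5 × 60/20 = 15 s.
- 12 to 40 per minute: shortest 3 × 60/40 = 4.5 s; longest 5 × 60/12 = 25 s.
- Rate at which the limit is just reached: 5 × 60/30 = 10 per minute for five cycles; 3 × 60/30 = 6 per minute for three.

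Across the assumed ranges the planned recording fits within 30 seconds. The wording in 4h and the cap in 8a and 8b therefore do not conflict on duration; the mismatch concerns only which step is said to wait.

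**The case for a change.** The strongest case for acting is that the compatible sequence is an inference. No passage writes it out, and none says whether the line is closed during recording. Section 3 describes reading pressure during drainage of effusions, so a site might do something similar here. The trial is multi-site with competitive enrolment, and the items listed in 4a would not reveal such a difference. A few sentences and one data field would cost almost nothing.

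Part of this stands. The order is inferred, the reason in 4h does not expressly cover the recording seconds, and the sentence in 8a about participation does not hold for the measurement delay.

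The rest does not carry. The documents contain no sign that sites would vent air before or during the reading, and 8a points the other way. Apart from the adverse event and deviation forms in 4d, the REDCap field list is not shown, so one cannot say that a given field is absent. The documents offer no means of sizing an effect on Ppl, on the t-test or on the secondary analyses. The 25 tension patients are a count of those to whom the argument in 4h is directed, not a measure of consequence.

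**Conclusion.** No change to the plan follows. The apparent contradiction arises by implication and disappears under a sequence that 4h, 8a and 8b all allow. The possible delay is openly stated, limited to 30 seconds, and backed by removal and standard care. On assumed rates of 12 to 40 breaths per minute the reading itself takes 4.5 to 25 seconds.

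What remains is editorial. Sections 4a, 4h and 8a must be reconciled in wording so that the order of steps reads the same throughout, and the delay in 8a belongs apart from the standard procedural risks. That is for the sponsor to word; nothing here says which clinical order is right. Such edits would leave the patients, the measurement, the outcomes and the analysis as they are.

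This conclusion assumes that sites take the single reading before evacuation, as 8a indicates, and that the assumed breathing rates are reasonable. Evidence that some sites vent air during recording would reopen the question of what the initial pressure means; the documents contain none.

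### Positive-pressure ventilation is not excluded and breathing mode at measurement is not specified as a data item, so pooled Ppl may mix different quantities and the SP-TP t-test can be confounded

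*Combined protocol and SAP*

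**What the plan says.** All references are to the combined protocol and SAP.

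- **Who enters.** Section 5 admits "patients aged 18 or older admitted with clinical or radiographic evidence of new pneumothorax who are referred to Interventional Pulmonology" for aspiration or tube thoracostomy. Section 4a gives the types: "Patients admitted with spontaneous, iatrogenic, or tension pneumothorax". Neither sets a condition on how the patient is breathing.
- **Who is kept out.** "Exclusion criteria include bilateral pneumothorax and pregnancy". Section 4j adds removal when Ppl cannot be measured reliably within 30 seconds. Ventilation, intubation and positive pressure are not mentioned in any section.
- **How the groups are formed.** "TP will be defined as a pneumothorax that results in mean arterial pressure <65 or systolic BP < 90". Group depends on blood pressure alone.
- **What is measured.** "Ppl will be recorded for 3-5 respiratory cycles" (4a). The primary outcome variables in 7a are "Inspiratory Ppl, Expiratory Ppl, and Mean Ppl".
- **What else is collected.** 4a lists tube indication, tube duration, pleurodesis, IBV and VATS referral, as examples of outcome data. Breathing mode is not among them.
- **How the groups are compared.** 7c plans a Student's t-test of Ppl between 100 SP and 25 TP patients, with no covariate, stratum or sensitivity analysis.

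**The concern.** The direction of the inspiratory pressure swing depends on breathing mode: pleural pressure falls in spontaneous inspiration and rises when the breath is driven by positive airway pressure. This is a physiological premise, not something the documents state. If both kinds of patient are enrolled, inspiratory Ppl is one variable name for two quantities, and mean Ppl inherits part of the mixture.

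Two things are at stake. The primary objective in Section 2 is to describe Ppl through the respiratory cycle, and a summary pooled over modes describes neither mode well. This holds even if SP and TP contain the same share of ventilated patients. Second, if the shares differ, part of any SP-TP difference in 7c comes from the ventilator. The abstract sets the study against a guideline definition of tension as Ppl above atmospheric pressure for much of the cycle. Positive-pressure ventilation moves Ppl in that same direction, so without breathing mode the two explanations could not be told apart.

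**Working it through.** **The plan's own figure.** 7c bases 100 SP and 25 TP on expected incidence. No alpha, power, effect size, SD or incidence is given, so the figure cannot be reproduced. For scale, with two-sided alpha 0.05 (assumed), the difference detectable with 80% power is

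(1.960 + 0.842) × √(1/100 + 1/25) = 2.802 × 0.2236 = 0.63 SD,

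or about 3.1 cmH2O if the SD is 5.

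**Inputs**
- From the documents: 100 SP, 25 TP, unadjusted t-test (7c).
- Assumed, because the documents are silent: two-sided alpha 0.05; within-group SD 5 cmH2O; 5% of SP ventilated; 5%, 20% or 40% of TP ventilated; ventilation raising Ppl by 2.5, 5 or 10 cmH2O (0.5, 1 or 2 SD), equally in both groups; no true SP-TP difference.

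**Step 1: effect on the pooled description.** A group's mean moves by share × shift. With 5% ventilated and a shift of 10, it moves by 0.05 × 10 = 0.5 cmH2O. With 40% and the same shift, it moves by 4 cmH2O.

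**Step 2: bias in the comparison.** Bias = (share in TP − share in SP) × shift. For example, (0.20 − 0.05) × 5 = 0.75 cmH2O, and (0.40 − 0.05) × 10 = 3.5 cmH2O. Equal shares give zero.

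**Step 3: false-positive rate.** The 7c t-test was simulated 100,000 times per row.

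| TP ventilated | Shift (cmH2O) | Bias (cmH2O) | False positives |
|---|---|---|---|
| 5% | 2.5, 5 or 10 | 0 | about 5% |
| 20% | 2.5 | 0.375 | 6.4% |
| 20% | 5 | 0.75 | 10.8% |
| 20% | 10 | 1.5 | 23.7% |
| 40% | 2.5 | 0.875 | 12.3% |
| 40% | 5 | 1.75 | 32.5% |
| 40% | 10 | 3.5 | 73.2% |

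The largest bias, 3.5 cmH2O, exceeds the 3.1 cmH2O that the study could detect. The smallest is negligible.

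**Step 4: the two sensitivity analyses.** Under the same assumptions, both a comparison in spontaneously breathing patients only and a linear model of Ppl on group plus a two-level mode term bring the false-positive rate back to about 5% in every row. This does not test for over-adjustment, because the simulation has no true difference and one common shift.

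**Step 5: precision of the restricted comparison.** With 20% of TP ventilated, about 95 SP and 20 TP remain: 2.802 × √(1/95 + 1/20) = 0.69 SD (3.4 cmH2O). With 40%, about 95 and 15 remain: 2.802 × √(1/95 + 1/15) = 0.78 SD (3.9 cmH2O).

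**The case against.** The strongest case on the other side has five parts.

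1. **Breathing mode may be recorded.** The 4a sentence is an open list of outcome data. It also omits blood pressure, which the TP definition requires, so it cannot be the whole data set, and the REDCap forms are not shown. This stands: a reader might infer that breathing mode is not recorded, but the documents support only that the plan does not specify it.
2. **Ventilated patients may not be enrolled.** Their eligibility follows from the absence of an exclusion, and the exclusion sentence is itself worded openly. This also stands. How many would enter is unknown. The silence still leaves sites and readers unable to tell whether they belong.
3. **Unequal shares are inferred.** It is reasonable to expect hypotensive patients to be ventilated more often, but nothing in the documents says so, and with equal shares the comparison has no bias. This stands, and is why the near-null rows are in the table.
4. **The stated objective is descriptive.** No objective claims a cause for an SP-TP difference. This limits the weight of the t-test result, but mixing modes affects the description too.
5. **Adjustment can do harm.** If tension leads to ventilation, or positive pressure helps to produce tension, a mode term may remove part of a real difference. This stands, and it rules out making the adjusted model the main analysis.

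**Conclusion.** The point holds as a gap in specification with a possible effect on the results. As written, the criteria do not exclude positive-pressure ventilation, breathing mode is not a specified data item, and 7c has no analysis that separates the modes. If both modes are enrolled, pooled inspiratory and mean Ppl mix different quantities. If the ventilated shares also differ, the SP-TP comparison is biased upward or downward with the sign of that difference.

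The size is illustrative only: a false-positive rate anywhere from about 5% to 73%, depending on shares, shift and SD, none of which the documents give. A reader might infer that the comparison is confounded, or that a raised Ppl in TP would be a ventilator effect. The documents do not support that; they show only that the plan could not rule it out. The point is best classed as a cheap improvement.

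**What to change.** - **4a:** add breathing mode at the time of measurement as a data item: spontaneous or positive pressure, with the type of positive pressure noted.
- **Description of the primary outcomes:** report inspiratory, expiratory and mean Ppl separately by mode.
- **7c:** keep the SP-TP comparison as planned and add two sensitivity analyses: (a) SP against TP in spontaneously breathing patients only; (b) a linear model of each Ppl measure on group plus a two-level breathing-mode term. Two levels are enough: with 20% of TP and 5% of SP ventilated, each group has only about 5 ventilated patients (0.20 × 25 and 0.05 × 100), too few to split by type.

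**Cost.** One extra REDCap field and two short analyses, with no change to the sample size. Intervals will be wider with at most 25 TP patients. Analysis (b) may over-adjust if ventilation is a cause or a consequence of tension, so it should be read beside the main comparison and not replace it. If few patients turn out to be ventilated, the field shows that and the pooled result is easier to defend.

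### The SP versus TP comparison names a Student's t-test at an expected 100:25 split with no basis for equal variances; Welch's test should be named instead

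*Combined protocol and SAP*

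**What the plan says.** Section 7c (Study Statistics) gives one method for comparing SP with TP: "A student's t-test will be used to determine statistical significance in differences of Ppl between SP and TP". Section 7a lists three primary outcome variables to which it would apply: inspiratory, expiratory and mean Ppl. The group sizes are given as "A sample size of 100 SP and 25 TP will be used based on expected incidence of disease in recruitment period".

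The protocol does not say whether the t-test pools the variances. It gives no SD for either group, no equal-variance assumption, no significance level and no alternative test.

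On what is known about the TP group, Section 1 says "these manometric definitions remain controversial as Ppl in TP has never been measured" and Section 3 says "Still to date, Ppl in TP have yet to be reported". Section 5 defines TP by blood pressure, so the definition does not limit how widely Ppl may vary within that group.

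The 100:25 split is an expectation. Section 7c adds "Enrollment will be competitive across all sites", and Section 4j says "Participant removal criteria include pneumothorax in which Ppl cannot be reliably measured within 30 seconds". Section 7d makes consistent failure to measure Ppl in TP a reason to stop early.

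The only primary objective, in Section 2, is to "Describe the intrapleural pressure throughout the respiratory cycle in patients with pneumothorax".

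**The concern.** Student's t-test usually means the pooled-variance form. That form is robust to unequal variances when the groups are about the same size, but not when one group is four times the other. The pooled variance then mostly reflects the large group, whereas the sampling error of the mean difference comes mostly from the small one. If TP pressures are more variable than SP pressures, the test rejects too often; if they are less variable, it rejects too rarely and loses power.

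By the protocol's own account there are no TP data from which to judge which case applies. This is the only planned SP–TP test, and it concerns the primary outcome variables. Its actual error rate would therefore depend on an unknown quantity. A confidence interval built on the same pooled standard error, if one were reported, would have the same fault.

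**Working it through.** **The plan's own figure.** The sizes of 100 and 25 are "based on expected incidence of disease in recruitment period". With no level, power, difference or SD behind them, they cannot be reproduced or contradicted statistically. As a back-calculation only, with equal SDs and a two-sided 5% level, 100 and 25 give 80% power for a difference of 0.63 SD.

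**Inputs**
- From Section 7c: 100 SP and 25 TP.
- Assumed, because the documents do not give them: pooled form, two-sided 5% level, normal data, and the SD ratio r = SD(TP)/SD(SP), shown over a range. The SP SD is set to 1.

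**Step 1: where the weight falls.** At r = 1, SP supplies 99/123 = 80% of the pooled variance. The true variance of the mean difference is 1/100 + r²/25, and the TP share of it is:
- r = 0.8: 0.0256/0.0356 = 72%
- r = 1: 0.04/0.05 = 80%
- r = 1.25: 0.0625/0.0725 = 86%

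**Step 2: closed-form approximation.** The pooled test in effect uses the variance [(99 + 24r²)/123] × (1/100 + 1/25). Its type I error is about 2 × [1 − Φ(1.96 × √(V_pooled/V_true))].
- r = 0.8: V_pooled = (114.36/123) × 0.05 = 0.0465; V_true = 0.0356; error about 2.5%.
- r = 1.25: V_pooled = (136.5/123) × 0.05 = 0.0555; V_true = 0.0725; error about 8.6%.
- r = 2: V_pooled = (195/123) × 0.05 = 0.0793; V_true = 0.17; error about 18.1%.

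**Step 3: numerical integration over the two sample variances.** Type I error (%) at 100:25:

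| r | 0.8 | 0.9 | 1 | 1.1 | 1.25 | 1.5 | 2 |
|---|---|---|---|---|---|---|---|
| Pooled | 2.6 | 3.7 | 5.0 | 6.4 | 8.6 | 12.2 | 18.0 |
| Welch | 5.0 | 5.0 | 5.0 | 5.0 | 5.0 | 5.0 | 5.0 |

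Separate simulations (400,000 trials per ratio) gave 8.7%, 12.1% and 18.0% for the pooled test at r = 1.25, 1.5 and 2. The imbalance is the cause: at 63 versus 62, the pooled test runs at 4.9% for r = 0.5 and 5.2% for r = 2.

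**Step 4: other achieved splits.** Pooled type I error (%):

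| SP:TP | r = 0.8 | r = 1.25 | r = 1.5 | r = 2 |
|---|---|---|---|---|
| 80:45 | 3.7 | 6.5 | 7.9 | 9.9 |
| 90:35 | 3.1 | 7.5 | 9.9 | 13.6 |
| 100:15 | 2.1 | 9.6 | 14.4 | 22.6 |

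Welch stays at 5.0% to 5.1% in all of these. A smaller TP group makes the pooled distortion worse, and a more even split reduces it.

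**Step 5: skewed data.** With skewness 1 at 100:25, for ratios 0.8 to 2, pooled runs from 2.5% to 18.0% and Welch from 5.1% to 5.5%. At 100:15 with the same skewness, Welch runs from 5.2% to 6.0% over ratios 0.5 to 2.

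**Step 6: price of Welch's test when the SDs are equal.** At 100:25 and a difference of 0.63 SD, power is 79.8% pooled and 78.3% Welch. At the difference where the pooled test has 80% power, Welch has:

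| SP:TP | 90:35 | 100:25 | 100:20 | 100:15 | 100:10 |
|---|---|---|---|---|---|
| Welch power (%) | 79.4 | 78.5 | 77.7 | 76.3 | 72.9 |

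**The case against.** The arithmetic is not in dispute. The objections concern how much follows from it.

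- **The fault is conditional.** The protocol does not say that variances will be pooled, so naming Welch's test may only clarify what is intended. Nor does a lack of TP data show that the variances differ; for ratios of 0.9 to 1.1 the error is only 3.7% to 6.4%. This stands. The larger figures are scenarios, and no direction can be claimed. It is still a reason to settle the form before the data are seen.
- **The objective is descriptive.** The SP–TP comparison is not listed among the objectives, and no confidence interval is planned. This limits the consequence to the significance test. That test is nevertheless planned, on the primary outcome variables.
- **Welch's test is not a complete cure.** With strong skewness (2, an assumption) it runs at about 5.8% to 7.2% at 100:25, against 2.7% to 18.4% for the pooled test. At 100:15 it reaches 6.9% to 8.6%. At 100:10 with equal SDs it is about 9%, while the pooled test is at 4.3% to 4.6%. This stands as a limit: the pooled form does clearly better near equal SDs with strong skew, mainly if TP recruitment falls far below 25. It does not change the preference at the planned sizes.
- **Extra summaries go beyond the defect.** Agreed; they are good reporting but not needed to correct the choice of test.

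**Conclusion.** The concern holds. At the expected 100:25 split, the usual form of the named test keeps its 5% level only if SP and TP have nearly equal SDs, and by the protocol's own account there are no TP data to support that. For illustrative SD ratios of 0.8 to 2, the actual error runs from 2.6% to 18.0%, against 5.0% for Welch's test. This rests on the pooled form being used, a two-sided 5% level, near-normal data and the split actually achieved. The true ratio, and so the direction and size of any distortion, is unknown.

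The consequence falls on the SP–TP significance test for each of the three Ppl measures, and not on the descriptive results. It is a change that should be made because it is cheap, rather than a flaw that undermines the study.

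**What to change.** In Section 7c, for SP versus TP only, replace Student's t-test with Welch's unequal-variance t-test.

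As optional reporting, for inspiratory, expiratory and mean Ppl, give each group's n, mean and SD, and the mean difference with its Welch 95% confidence interval. Readers can then see the spread in each group for themselves.

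Do not extend the change automatically to the comparisons by pleurodesis, IBV, VATS and chest tube duration. The expected event counts are not given, and Welch's test can lose considerable power when one group is very small.

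The cost is a few words and no extra patients or data. If the SDs turn out equal, about 1.5 points of power are lost at 100:25. The loss becomes material only if TP recruitment falls far short, for example from 80% to 72.9% at 100:10.
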